15. ADVERSE EVENT REPORTING

Adverse event is any untoward medical occurrence that may present during treatment with a pharmaceutical product but which does not necessarily have a causal relationship with this treatment.

Adverse drug reaction is a response to a drug which is noxious and unintended and which occurs at doses normally used in man for prophylaxis, diagnosis, or therapy of disease or for the modification of physiologic function.

Assessing causal connections between agents and disease is fundamental to the understanding of adverse drug reactions. In general, a drug may be considered a contributory cause of an adverse event if, had the drug not been administered, 1) the event would not have happened at all, 2) the event would have occurred later than it actually did, or 3) the event would have been less severe.

15.1 Adverse Event Reporting

Protocol: ARO-005

The Investigator or physician designee is responsible for verifying and providing source documentation for all adverse events and assigning the attribution for each event for all subjects enrolled on the trial.

For clarity the information required by the sponsor at baseline is to be captured in the CRFs is:

Forms Title	Content to be captured
'Relevant Medical History' (SC_5_Screening)	Any prior important medical history
'Physical Examination' (SC_6_Screening)	From physical examination during screening
'Baseline Medical history' (SC_7_Screening)	Any current medical history
'Baseline Symptoms' (SC_8_Screening)	Any current symptoms

Table 15.1. Sponsor-Required Baseline Information in CRFs.

Adverse Events (AEs) will be evaluated according to the latest CTCAE version 4.03 and documented in medical record. Principal investigator should review and provide documentation of all baseline comorbidites related to the preexisting conditions and/or current medications prior to initiation of cycle one. These events will not be considered as related to crenolanib treatment. If these events continue during the treatment phase they do not need to be captured in the case report form. Captured AEs include:

- 1) Any new AE regardless of its grade or expectedness post study drug initiation
- 2) Worsening of any expected or unexpected AEs determined by the principal investigator as related to crenolanib

Expected events during leukemia therapy are (all other are considered unexpected and should be captured for reporting as outlined above):

- 1) Febrile or infection episodes
- 2) Coagulation abnormalities
- 3) Epistaxis or bleeding except for catastrophic CNS or pulmonary hemorrhage
- 4) Preexisting side effects related to prior disease specific therapy or ongoing medications for management of non-leukemia conditions
- 5) Myelosuppression and myelosuppression-related events (due to disease)
- 6) Bone, joint, or muscle pain
- 7) Fatigue/malaise
- 8) Weakness
- 9) Shortness of breath
- 10) Nausea and vomiting
- 11) Anorexia
- 12) Electrolyte abnormalities (sodium, potassium, bicarbonate, CO2, magnesium)
- 13) Chemistry abnormalities (LDH, phosphorus, calcium, BUN, protein, albumin, uric acid, alkaline phosphatase, glucose)
- 14) Coagulation abnormalities
- 15) Alopecia

Protocol: ARO-005

General Therapy Related Events:

- 1) Catheter related events (thrombosis, bleeding, infection)
- 2) Renal failure related to tumor lysis syndrome or antibiotic/ antifungal therapy
- 3) Rash related to antibiotic use
- 4) Hospitalization for the management of any of the above expected events

Reporting Hematology and Blood Chemistry Results:

- Hematology and blood chemistry results for every scheduled visit or for the most contiguous to the scheduled visit should be reported on case report form. Data captured in addition to the protocol specified scheduled visit is to be captured, only if any abnormal hematological or chemical values resulted in dose modification or dose delay.
- Transfusion information is to be captured throughout the study.

Adverse Event Reporting in 30-day Follow-up Period:

- Adverse events will be captured from the time the patient signs consent until 30 days after the last dose of study drug.
- If patients goes on to another clinical study or standard therapy, if possible, adverse events should continue to be captured for 30 days, including name of new therapy.
- Patients who do not have progressive disease but stop crenolanib for toxicity, should be followed until resolution of toxicity.

 Patients who have progressive disease and do not receive further therapy do not need to be followed, unless there is toxicity related to study drug which is unresolved at the time patient is taken off study

15.2 Serious Adverse Event (SAE) Reporting:

A serious adverse event is – any adverse drug experience occurring at any dose that results in any of the following outcomes:

Death

Protocol: ARO-005

- A life-threatening adverse drug experience any adverse experience that places the patient, in the view of the initial reporter, at immediate risk of death from the adverse experience as it occurred. It does not include an adverse experience that, had it occurred in a more severe form, might have caused death.
- Inpatient hospitalization or prolongation of existing hospitalization
- A persistent or significant disability/incapacity a substantial disruption of a person's ability to conduct normal life functions.
- A pregnancy or congenital anomaly/birth defect.
- Important medical events that do not result in death, be life-threatening, or require hospitalization may be considered a serious adverse drug experience when, based upon appropriate medical judgment, they may jeopardize the patient or subject and may require medical or surgical intervention to prevent one of the outcomes listed in this definition. Examples of such medical events include allergic bronchospasm requiring intensive treatment in an emergency room or at home, blood dyscrasias or convulsions that do not result in inpatient hospitalization, or the development of drug dependency or drug abuse (21 CFR 312.32).

Any important medical event may be reported as an SAE if deemed appropriate by the Principal Investigator and the IND Sponsor. .

All serious adverse events occurring during the conduct of a protocol will be reported (either via expedited report or log) to the IRB in accordance with the timeframes and procedures.

All serious adverse events will be recorded in the case report form.

Hospitalizations for the management of any expected adverse events (previously described) will be reported to the sponsor as SAE and follow SAE reporting requirements

- All life-threatening or fatal events, expected or unexpected, and regardless of attribution to the study drug, must have a written report submitted within 24 hours (next working day) of knowledge of the event to AROG.
- The institution's Internal SAE Report Form for Prompt Reporting will be used for reporting to AROG
- Serious adverse events will be captured from the time the patient signs consent until 30 days after the last dose of drug. Serious adverse events must be followed until clinical recovery is

complete and laboratory tests have returned to baseline, progression of the event has stabilized, or there has been acceptable resolution of the event.

Additionally, any serious adverse event that occur after the 30 day time period that is related to the study treatment must be reported to IRB and to AROG. This may include the development of a secondary malignancy.

15.3 Reporting to FDA:

Protocol: ARO-005

Serious adverse events will be forwarded to FDA by the IND Sponsor (AROG) according to 21 CFR 312.32.

It is the responsibility of the PI and the research teams to ensure serious adverse events are reported according to the Code of Federal Regulations, Good Clinical Practices, the protocol guidelines, the sponsor's guidelines, and Institutional Review Board policy.

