5. CRENOLANIB BESYLATE (CP-868,596-26), CLINICAL DATA

Phase I/II clinical study of oral crenolanib showed that it was well absorbed and well tolerated

Crenolanib has been clinically evaluated as a single agent in a dose-finding and dose-ranging phase-1 study with fifty nine patients treated and was found to have good oral bioavailability. Crenolanib was rapidly absorbed on an empty stomach with a median t_{max} ranging from 1 to 4 hours. The half-life of crenolanib in this Phase I trial was found to be between 13-16 hours.

As of 31 May 2013, no treatment related deaths have been reported in 200 patients treated with crenolanib both as a single agent and in combination. The most frequent non-hematological grade 1/2 toxicities were diarrhea, nausea, and vomiting (Table 5.1). In patients with GIST, anemia was the most frequent grade 1/2 hematological toxicity associated with crenolanib treatment. Four patients required transfusion, though most of these patients had grade 1/2 anemia prior to treatment initiation. The most commonly reported all-causality events of severity Grades 3 or 4 have included LFT increase, anemia, hyponatremia, fatigue and headache.. All LFT abnormalities resolved to baseline or less upon discontinuation of crenolanib. The AML protocol recommends prophylactic antiemetics and anti-diarrheals as well as regular monitoring of hepatic enzymes. Table 5.1 summarizes AEs observed in 126 adult and pediatric patients treated with single agent crenolanib.

Confidential

Protocol: ARO-005

19

		NCI CTC S	Total patients = 126			
Advance Event	GRADE	GRADE	GRADE	GRADE	TOTAL	%
Adverse Event	1	2	3	4	AEs	Patients
Nausea	86	19	2	1	108	63
Vomiting	85	10	4	0	99	55
Diarrhea	62	13	1	0	76	45
Alanine aminotransferase						
increased	32	9	7	2	50	23
GGT increased	33	14	13	3	63	21
Fatigue	16	12	2	0	30	18
Alkaline phosphatase increased	25	10	2	0	37	14
Anorexia	15	5	1	0	21	13
Aspartate aminotransferase						
increased	28	11	6	2	47	13
Lymphocyte count decreased	22	10	7	2	41	13
Headache	14	1	2	0	17	10
Anemia	8	6	4	2	20	10
Abdominal pain	11	2	2	0	15	10
Dyspepsia	7	4	2	0	13	10
Dysgeusia	11	3	0	0	14	9
Constipation	11	2	0	0	13	9
White blood cell decreased	16	4	1	0	21	8
Proteinuria	12	0	0	0	12	7
Edema limbs	11	2	0	0	13	6
Hypophosphatemia	10	0	1	0	11	6
Hypoalbuminemia	8	0	0	0	8	6
Periorbital edema	8	0	0	0	8	6
Serum amylase increased	4	3	0	0	7	6
Dizziness	7	0	0	0	7	5
Platelet count decreased	4	0	0	2	6	5

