16. STATISTICAL CONSIDERATIONS

16.1 Determination of Sample Size

The primary endpoint of the study is the overall response rate to crenolanib. The outcome may be different for patients with or without the previous FLT3 TKI therapy. Therefore, patients will be stratified according to whether they have recurred after prior chemotherapy without a FLT3 TKI treatment or they have progressed after prior therapy with a FLT3 TKIs.

Based on the promising results observed to date, the sample size for each cohort will be expanded to include a total of 30 patients in Cohort A and 40 patients in Cohort B. Such additional patients will permit a more accurate assessment of the efficacy and safety of crenolanib in these populations. The total sample size for the two cohorts is 70 patients.

Cohort B (N=40): Two parallel Simon minimax two-stage Phase II designs will be used for the two cohorts of patients. For the patients who progressed after prior chemotherapy with FLT3 TKI, the null response rate will be 5%, and target response rate will be 20%. With alpha of 0.05 and beta of 0.08, the first stage will require 28 patients. If there is 1 or no patient responding, the trial will be stopped. If 2 or more out of the first 28 patients respond, accrual will continue until a total of 40 patients have been enrolled. At the end of the study, if 5 or more patients out of 40 respond, the regimen will be considered active. With this design, the probability of early termination is 59% if the true response rate is only 5%.

Cohort A (N=30): For the patients who progressed after prior chemotherapy without FLT3 TKI, the null response rate will be 5%, and target response rate will be 30. With alpha of 0.06 and beta of 0.01, the first stage will require 24 patients. If there is 1 or no patient experiencing the response, the trial will be stopped. If 2 or more out of the first 24 patients respond, accrual will continue until a total of 30 patients have been enrolled. At the end of the study, if 4 or more patients out of 30 respond, the regimen will be considered active. With this design, the probability of early termination is 66% if the true response rate is only 5%.

The method of Thall, Simon, and Estey will be employed to perform interim safety monitoring. We will assume a Beta (0.6, 1.4) prior distribution for the toxicity rate which in particular has mean of 30%. The toxicity is defined as any grade 3 or greater non-hematologic toxicities attributed to the study drug.

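### Section 15.1 gives two incompatible signals on whether listed, expected adverse events must be captured; this mainly exposes the adverse event tables and, to a lesser degree, the section 16.1 toxicity count

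*Combined protocol and SAP*

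**What the plan says.** Section 15.1 defines the captured adverse events by two items. Item 1 is "Any new AE regardless of its grade or expectedness post study drug initiation". Item 2 is "Worsening of any expected or unexpected AEs determined by the principal investigator as related to crenolanib". The only express CRF exemption in that section is for baseline conditions that continue during treatment.

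The list that follows is introduced by "Expected events during leukemia therapy are (all other are considered unexpected and should be captured for reporting as outlined above". It includes "Nausea and vomiting", "Fatigue/malaise", anorexia, and "Chemistry abnormalities (LDH, phosphorus, calcium, BUN, protein, albumin, uric acid, alkaline phosphatase, glucose". These entries carry no limit to disease-related cases, whereas the myelosuppression entry does.

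Section 5 reports that "The most frequent non-hematological grade 1/2 toxicities were diarrhea, nausea, and vomiting", and Table 5.1 gives the related events by type and grade.

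For the stopping rule, section 16.1 states: "The toxicity is defined as any grade 3 or greater non-hematologic toxicities attributed to the study drug". It makes no exception for expected events.

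**The concern.** If item 1 governs, the phrase in the list heading that singles out all other events for capture has no function. If the heading governs, item 1 is wrong where it says that expectedness does not matter. A site coordinator could reasonably follow either.

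Two things are at stake. First, safety and tolerability is a primary objective (section 1.1), and sites reading the text differently would produce adverse event rates that cannot be pooled or compared. Second, section 16.1 counts drug-attributed grade 3 or greater non-hematologic toxicities, and some of these are of listed types. An event that is never entered as an adverse event with grade and attribution may never reach that count.

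**Working it through.** **1. Which toxicities are on the list.** Percentages of the 126 patients, from Table 5.1:

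| On the list | Not on the list |
|---|---|
| Nausea 63, vomiting 55, fatigue 18, alkaline phosphatase 14, anorexia 13, hypophosphatemia 6, hypoalbuminemia 6 | Diarrhea 45, ALT 23, GGT 21, AST 13 (and the lesser terms) |

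The list holds the two commonest toxicities but not the third to fifth.

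**2. Share of all related events.** All rows of Table 5.1 sum to 757 events. Removing the hematologic rows (lymphocytes 41, anemia 20, white cells 21, platelets 6; total 88) leaves 757 − 88 = 669. Listed types: 108 + 99 + 30 + 37 + 21 + 11 + 8 = 314. The share is 314/669 = 47%.

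**3. Share of grade 3-4 events.** Non-hematologic grade 3-4 events: nausea 3, vomiting 4, diarrhea 1, ALT 9, GGT 16, fatigue 2, alkaline phosphatase 2, anorexia 1, AST 8, headache 2, abdominal pain 2, dyspepsia 2, hypophosphatemia 1; total 53. Listed types: 3 + 4 + 2 + 2 + 1 + 1 = 13, or 13/53 = 24.5%. Of the other 40, 33 are ALT, GGT or AST. The all-grade tables are therefore more exposed than the stopping-rule count.

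**4. Reproducing the plan's rule.** The boundary at n patients is the smallest x with P(Beta(0.6 + x, 1.4 + n − x) > 0.30) > 0.93. At n = 5, 10, ..., 65 this returns all 13 values of Table 16.1. An exact binomial recursion to 70 patients, with looks every 5, reproduces Table 16.2:

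| True rate | Stopping probability | Mean patients |
|---|---|---|
| 0.20 | 0.016 | 69.1 |
| 0.25 | 0.059 | 67.0 |
| 0.30 | 0.183 | 61.8 |
| 0.35 | 0.423 | 52.2 |
| 0.40 | 0.705 | 39.9 |
| 0.50 | 0.979 | 20.4 |

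**5. Effect of lost patients.** Let f be the share of qualifying patients whose only qualifying toxicity goes unrecorded. The rule then sees p × (1 − f). The documents do not give f, so the values below are assumptions. With p = 0.40:

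| Assumed f | Rate seen | Stopping probability | Mean patients |
|---|---|---|---|
| 0 | 0.400 | 0.71 | 39.9 |
| 2/53 ≈ 4% | 0.385 | 0.62 | 43.7 |
| 10% | 0.360 | 0.48 | 49.9 |
| 13/53 ≈ 25% | 0.302 | 0.19 | 61.5 |

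The 4% case loses only the two fatigue events. The 25% case loses every listed grade 3-4 event at every site.

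**The case against.** The strongest reply is that section 15.1 never forbids capture of listed events. The word *only* is absent, and the heading refers back to the rule above it, which takes every new event. Other text points the same way: source documentation and attribution for all adverse events (15.1), capture from consent to 30 days after the last dose with no limit by expectedness (15.1), and adverse events at every visit in Appendix V. This stands in part. A reader might infer an explicit instruction to omit listed events, and the documents do not support that. They contain an ambiguity in which one sentence implies an exemption that another denies.

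The second reply concerns backstops. Section 15.2 puts all SAEs in the CRF and makes hospitalization for an expected event an SAE. Item 2 captures worsening judged related to crenolanib. Scheduled chemistry results also go on the CRF. Of the 13 listed grade 3-4 events, eight are vomiting, nausea or anorexia, for which the grade 3 definitions in Appendix VII include a need for tube feeding or TPN and, for nausea and vomiting, hospitalization. Three are laboratory findings whose values would be visible. This narrows the exposure but does not remove it. By Appendix VII, grade 3 fatigue that limits self-care, grade 3 nausea with inadequate intake, or six or more vomiting episodes in a day need not involve admission, and a laboratory value on the CRF carries no attribution.

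Third, section 16.1 does not say that the count is drawn from CRF adverse event entries alone. That is correct, so the link to the stopping rule is a risk and not a demonstrated loss.

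**Conclusion.** The inconsistency is real and should be resolved. Its main consequence is for the adverse event tables, where types making up 47% of historical non-hematologic related events could be recorded at one site and omitted at another when not serious. The stopping-rule consequence is confined to new, non-serious, drug-attributed grade 3 or greater events of listed types.

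Three stronger readings are tempting and not supported:

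- **That the stopping probability at a true rate of 0.40 falls to 0.19.** This requires every site to adopt the exempting reading, every listed event to be lost, and no help from section 15.2. It is the far end of an assumed range that starts at 0.71 (no loss) and passes through 0.62 and 0.48.
- **That 25% bounds the share of patients lost.** It is a share of events. ALT, GGT and AST events may cluster in the same patients, so the patient share could be higher or lower. Table 5.1 also covers a mixed adult and pediatric population and only terms at 5% or more.
- **That the Bayesian rule is the only numerical toxicity stop.** The synopsis also halts accrual if unacceptable toxicity exceeds 30% of patients.

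**What to change.** Replace the parenthesis in the section 15.1 list heading with a statement to this effect: *This list classifies expectedness only. All new adverse events, listed or not, are recorded in the CRF with grade and attribution, as item 1 requires. Listed events that meet the section 16.1 toxicity definition count toward the stopping rule.*

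This is one sentence's worth of amendment plus a reminder to sites. The downside is some additional CRF entries, which item 1 already asks for. It changes no dose or treatment rule.

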The anticipated duration of patient involvement is a minimum of 28 days with a maximum of 365 days but assessed individually for each patient. Patients will take crenolanib besylate daily until their disease has progressed, the patient has died, or the patient discontinues for adverse events, investigator's judgment, or other reasons

Patients who have discontinued study drug will continue to be followed for 30-days post last dose.

Reference Therapy, Dose and Mode of Administration:

No comparators will be used.

Criteria for Evaluation:

International Working Group for AML (Cheson, et. al., JCO, 2003)

Statistical Methods:

Protocol: ARO-005

The primary end-point is overall response rate. The overall response rates in the two cohorts will be evaluated along with its 95% confidence interval at the end of cycle 1 (28-days) and at best response. Analysis of secondary endpoints will be predominantly descriptive statistics and will be interpreted as being exploratory and hypothesis generating. Duration of response, Progression Free Survival (PFS) and Overall Survival (OS) will be estimated using the method of Kaplan-Meier. In addition, if at any time unacceptable toxicity is encountered in greater than 30% of patients, accrual will be stopped and lower doses of crenolanib may be investigated.

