7. STUDY DESIGN

This is a Phase II open label study of crenolanib besylate given at 100 mg TID (preferably every eight hours) continuously until one of the criteria for study discontinuation is fulfilled. Study drug should be taken at least 30 minutes prior to or following a meal. Patients will complete a daily diary to record the date, time, and amount (number of tablets) of crenolanib taken and relation to eating schedule (Appendix IV).

The study will enroll 2 different cohorts of patients in parallel.

Cohort A: Will enroll AML patients with FLT3 activating mutations who have progressed on one or more prior chemotherapy regimen who have not received previously a FLT3 TKI

Cohort B: Will enroll AML patients with FLT3 activating mutations whose leukemia has progressed and have received prior therapy with one or more FLT3 TKIs.

Cycles will be repeated approximately every 28 days, and therapy will be continued until clinically significant disease progression or documentation of unacceptable toxicity as determined by the investigator. If the drug is discontinued for toxicity, patient should be reassessed until toxicity has resolved.

In the setting where hematopoietic stem cell transplant is anticipated study drug will be discontinued at least 72 hours prior to start of conditioning.

Counting Cycle Days: If drug is held or a dose missed, the missed/held dose should not be made up. Dosing will resume with the next scheduled dose. The patient should enter in the diary the doses missed. If drug is held for a day or more, the counting of cycle days should continue as if uninterrupted. The start of cycle 1 is denoted by the ingestion of study drug. The scheduled procedures/visits should comply with the study calendar regardless of amount of study drug administered in a 28 day cycle.

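### Section 15.1 exempts untreated progressors from follow-up under a 30-day heading, contradicting the unqualified 30-day adverse event rules and making late safety capture depend on outcome

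*Combined protocol and SAP*

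**What the plan says.** Three places set a 30-day period after the last dose and attach no condition to it.

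- Synopsis, planned duration of treatment: "Patients who have discontinued study drug will continue to be followed for 30-days post last dose".
- Section 15.1, first bullet on the 30-day follow-up period: "Adverse events will be captured from the time the patient signs consent until 30 days after the last dose of study drug".
- Section 15.2, serious adverse events: "Serious adverse events will be captured from the time the patient signs consent until 30 days after the last dose of drug".

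Appendix V also marks adverse and serious adverse events at a follow-up visit, but neither the table nor its footnotes date that visit.

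The remaining bullets under the Section 15.1 heading treat patients differently by outcome. For those who move to another study or standard therapy, "adverse events should continue to be captured for 30 days, including name of new therapy", subject to a proviso that this is possible. Patients without progression who stop for toxicity are followed until it resolves. For the last group: "Patients who have progressive disease and do not receive further therapy do not need to be followed". That bullet makes a single exception, for crenolanib-related toxicity that is still open when the patient leaves the study. Section 15.2 contains no matching exemption for serious events. It adds that "any serious adverse event that occur after the 30 day time period that is related to the study treatment must be reported".

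**The concern.** A site cannot apply both the unconditional 30-day rule and a literal reading of the last bullet. If it follows the bullet, nobody looks for a new event arising in an untreated progressor after the patient goes off study. The exception does not close the gap, because it covers only drug-related toxicity already present and unresolved at that moment.

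The loss would not be random. Whether a late event is seen would depend on progression and on whether the patient went on to further therapy, and both are related to how ill the patient is. Progression is the first reason for stopping listed in Section 9.4, so the exempt group need not be rare. Safety and tolerability is a primary objective, and the trial has no comparator arm against which uneven capture would show up.

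**Working it through.** The main check is textual.

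| Place | Who | What | Until | Exception |
|---|---|---|---|---|
| Synopsis | all who stop drug | follow-up | day 30 | none |
| 15.1, first bullet | all | adverse events | day 30 | none |
| 15.2 | all | serious events | day 30 | none; related events also after day 30 |
| Appendix V | all | both | follow-up visit, undated | none |
| 15.1, new-therapy bullet | other study or standard therapy | adverse events | day 30 | only where possible |
| 15.1, last bullet | progressed, no further therapy | follow-up | not required | unresolved drug-related toxicity |

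So there are three explicit 30-day statements plus one undated visit. The last row conflicts with them if its follow-up means the 30-day follow-up. The synopsis uses the same verb for the 30-day period, and the bullet sits under a 30-day heading, so that reading is natural.

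Next, could the unobserved days matter for crenolanib? Section 5 gives a half-life of 13 to 16 hours in the phase I trial. Section 8.1 uses five half-lives as the washout for prior FLT3 inhibitors. Borrowing that yardstick: 5 × 13 = 65 hours and 5 × 16 = 80 hours, or about 2.7 to 3.3 days. Some exposure therefore continues into the period that would go unobserved.

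The plan's figures most directly exposed to missed late toxicity are those of the safety stopping rule in Section 16.1. Inputs: a Beta(0.6, 1.4) prior, a 30% toxicity limit, a cut-off of 0.93, and at most 70 patients. With t toxicities in n patients, the rule stops if Pr(rate > 0.30) > 0.93 under Beta(0.6 + t, 1.4 + n − t).

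- Table 16.1: at n = 5, t = 4 gives 0.9751 (stop) and t = 3 gives 0.8745 (continue). At n = 65, t = 26 gives 0.9521 and t = 25 gives 0.9205. All 13 boundaries reproduce.
- Table 16.2: an exact binomial recursion with looks every 5 patients from 5 to 65 gives stopping probabilities 0.016, 0.059, 0.183, 0.423, 0.705 and 0.979 at true rates 0.20, 0.25, 0.30, 0.35, 0.40 and 0.50. Average sample sizes are 69.1, 67.0, 61.8, 52.2, 39.9 and 20.4. All match.

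Now suppose a share m of patients with a qualifying toxicity is missed, so that the observed rate is p × (1 − m). The documents give no value for m; 5%, 10% and 20% are assumptions.

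| True rate p | m = 0 | m = 5% | m = 10% | m = 20% |
|---|---|---|---|---|
| 0.35 | 0.42 | 0.33 | 0.24 | 0.12 |
| 0.40 | 0.71 | 0.60 | 0.48 | 0.27 |
| 0.50 | 0.98 | 0.95 | 0.90 | 0.71 |

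For example, 0.40 × 0.95 = 0.38 gives 0.597, and 0.40 × 0.80 = 0.32 gives 0.267. The table shows direction and sensitivity; it does not estimate what this trial would lose.

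**The case against.** The strongest reply is that the last bullet is not about capture at all. The first two bullets concern capturing events; the last two concern following patients. The third follows patients without progression until toxicity resolves, and the fourth reads as its counterpart for progressors. Its exception for unresolved drug-related toxicity makes most sense as a follow-to-resolution rule. Section 15.2 draws the same line between capturing serious events to day 30 and following them to recovery. On this reading nothing is waived within the 30 days. The reading is plausible, but the bullet does not state it, and its heading and the synopsis wording point the other way. The conflict for sites remains.

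Four stronger inferences are tempting, and the documents do not support them.

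- *Deaths and serious events are shown to be under-counted.* Section 15.2 has no exemption for serious events, and Appendix VIII keeps events unequivocally due to progression out of serious event reporting. An under-count is a risk under one reading.
- *The 24-hour rule for fatal events cannot work.* That clock runs from knowledge of the event, so it works whenever the site learns of one.
- *Late data are kept for patients on new therapy and so mixed with other regimens' toxicity.* Capture there is only where possible. The new therapy is named, every event is attributed, concomitant medication carries start and stop dates (Section 16.4), and the stopping rule counts only toxicity attributed to crenolanib. Some mixing could remain in the overall summary of Section 16.4, which plans no split at new therapy, but an all-events window is defensible in a descriptive single-arm study.
- *Ninety percent of the window falls under transplant conditioning.* Section 7 says "study drug will be discontinued at least 72 hours prior to start of conditioning". A patient stopping at that minimum would have 30 − 3 = 27 of 30 days, or 90%, from the start of conditioning onward. That is one hypothetical extreme, the text sets only a minimum, and the Section 15.1 bullet does not name transplant. It does not measure the size of the problem.

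**Conclusion.** The point holds as an unresolved contradiction. Under the literal reading, new-onset events in untreated progressors are not sought within 30 days of last dose, and late safety capture depends on outcome. Under the follow-to-resolution reading there is no loss, but the text does not say which is meant, and sites may differ.

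The size cannot be determined. The documents do not give the share of patients who progress and receive no further therapy, or how often a first qualifying toxicity arises after the drug stops. The stopping-rule figures rest on assumed losses of 5% to 20%. Much toxicity will occur on drug, where the bullet does not apply, so they should not be read as estimates. With full capture, Table 16.2 stands unchanged. The correction is worth making because it is cheap and protects a primary objective.

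**What to change.** Reconcile the passages in Section 15.1. State that capture of adverse events, serious adverse events and deaths to 30 days after last dose applies to every patient, whatever the reason for stopping and whether or not new therapy starts, and that the exemption for progressors limits only follow-up beyond day 30. Date the Appendix V follow-up visit to match. A phone contact is enough for patients who cannot attend. The cost is one sentence, one footnote and a few more event records from progressors.

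Optionally, use the start date of any new anti-leukemic therapy to show adverse events with onset before and after that date separately, as a supplement to the overall summary in Section 16.4 and not a replacement for it. First confirm that the concomitant medication form records that date for new anti-leukemic therapy; if it does not, one date field is needed.
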